1. SUMMARY

Rationale: Fetal and neonatal alloimmune thrombocytopenia (FNAIT) is a disease caused by allo-immunisation during pregnancy. If left untreated, FNAIT can lead to severe fetal intracranial haemorrhage. This complication can be prevented by weekly administration of intravenous immunoglobulin (IVIg) to the mother during pregnancy. Although treatment with IVIg is nowadays considered as the golden standard for the management of FNAIT, the exact mechanism of action of IVIg is still under debate. Most importantly, the long-term effects and safety of IVIg treatment in FNAIT have not yet been evaluated. The use of IVIg during pregnancy for FNAIT is therefore still 'off-label'. The medication leaflet of IVIg continues to state that there is insufficient knowledge on the use of this product during pregnancy, despite all the years of experience and implementation in virtually all international guidelines.

Knowledge on long-term development of FNAIT survivors with or without IVIg treatment is very limited but an important subject in the counselling of parents of newly diagnosed cases. A greater understanding of the long-term outcome and the effects of IVIg on child development is necessary.

Objective: To evaluate the long-term neurodevelopmental outcome in two groups of children with FNAIT. First, children with unanticipated disease 'index cases' that were born without maternal IVIg administration during pregnancy. Second, children with anticipated disease; their mothers were treated with IVIg during pregnancy.

Study design: Observational cohort study.

Study population: The study population consists of two different cohorts of FNAIT children born in the Netherlands between 2002 and 2017.

- Cohort 1: The first cohort of children will consist children with unanticipated disease, 'index cases that were born without maternal IVIg administration during pregnancy.'
- Cohort 2: Second cohort will consist of children with anticipated disease; their mothers were treated with IVIg during pregnancy.

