No long-term standardized follow-up studies were performed on FNAIT cases without antenatal treatment and/or ICH. The natural course of the disease and long-term effects of thrombocytopenia on the developing fetus and newborn are unknown. FNAIT is defined as a disease caused by alloantibodies, resulting in thrombocytopenia and a risk of bleeding in the neonate. In the last years, evidence is increasing that the maternal alloantibodies can also bind to the fetal endothelium and may impair angiogenesis in the developing fetuses [8] [9]. It

is not known at which moment in pregnancy the developing brain is most vulnerable for damage induced by these kind of alloantibodies. The timing in fetal life FNAIT associated ICH ranges from 23 to 42 weeks [10], but small bleeding may not be diagnosed. It may also be that these type of alloantibodies not lead to ICH but to other type of cerebral damage. These lesions can remain subclinical directly after birth but lead to developmental delay on the long term. This knowledge can be of great interest when counseling parents with a risk of FNAIT or in writing guidelines.

For 3 decades a nationwide screening on FNAIT to detect pregnancies with alloantibodies in time and start treatment to prevent bleedings is being discussed. If alloantibodies lead to cerebral damage on the long term also in patients without large ICH this might have large implications in the debate on the introduction of a national screening programme. Therefore we want to underline that more knowledge about the long-term development of FNAIT survivors is required.

The Leiden University Medical Center (LUMC), a national fetal therapy center in The Netherlands, has a close and long-lasting collaboration with Sanquin. This collaboration offers a unique opportunity to evaluate a large and complete cohort of children with FNAIT. LUMC and Sanquin are both nationwide referral centers for FNAIT and committed to improve timely detection of high-risk cases who need intra-uterine therapy. In our opinion we have a duty as a national expertise center to assess long-term outcome in children with FNAIT and describe the natural history of children affected by FNAIT and the long term effects of a given therapy.

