3.3 Other study parameters

We will gather the data about the following data of our cases; age and sex of the child, obstetric medical data and neonatal characteristics and morbidity of the study population. Parents will be asked to complete a questionnaire to assess the highest level of education of the parents. We use this data to describe our study population and correct for potential confounding of these factors on neurodevelopmental outcome as described in chapter 11. Study parameters are summarized in Table 1, a list of definitions can be found in Table 3.

Possible confounding factors for allergies are the family history for asthma, allergies or eczema. For evaluation of the infections it is important to assess smoking at home and day-care visit as possible confounding factors.

Table 1: Study parameters

Study parameters		
Obstetric data	Maternal characteristics	Age mother at delivery Obstetric history Medication usage during pregnancy
	Pregnancy characteristics	Gravidity/Parity Pregnancy induced hypertension Pre-eclampsia Signs of bleeding in the fetus at ultrasound
	FNAIT related therapy	IVIg treatment Intra-uterine transfusions Treatment with corticosteroids
	Labour characteristics	Mode parturition Gestational age at delivery
	Placental features	Placenta weight
Neonatal data	Birth data	Gestational age at birth Birthweight Apgar score
	Severe neonatal morbidity	Respiratory distress syndrome Perinatal asphyxia Proven early onset neonatal sepsis Retinopathy of prematurity Necrotizing enterocolitis
	Neonatal neurologic sequelae	Intracranial haemorrhage Cystic periventricular leukomalacia Ventricular dilatation Porencephalic or parenchymal cysts Convulsions Any cerebral lesions associated with adverse neurologic outcome
	Signs of bleeding	Skin manifestations Intracerebral bleeding Organ bleeding Increased bleeding tendency, reported by the caregiver
	Therapy	Platelet transfusions IVIg treatment

Table 1: Study parameters

[figure not shown]
Study parameters		
Laboratory data	HPA	HPA incompatibility HPA genotyping Anti-HPA-titre Platelet count Directly after birth Nadir Other Presence of HLA class I antibodies

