11. STATISTICAL ANALYSIS

Continuous parametric data will be presented with mean \pm standard deviation (SD) or median with interquartile range (IQR) as appropriate. Categorical data will be presented as counts and percentages within each study group.

The cognitive test score of both cohorts will be compared with the Dutch average by using a linear regression model. The following potential confounders for cognitive development (IQ score) identified in earlier research will be used in the analysis;

- Sex
- Gestational age at birth
- Small for gestational age
- Neonatal morbidity
- Level of education of the parents

In second cohort; the FNAIT survivors with IVIg treatment atopic constitution and the course of infections will be assessed in a secondary analysis.

In the assessment of course of infections the following confounders will be used in the analysis by using a linear regression model;

- Day-care visit
- Smoking in a household
- Time of the year that the questionnaire was filled in

In the analysis of allergies and asthma the following confounders will be used in the analysis by using a linear regression model;

- Presence of a first degree family member with asthma eczema or allergy
- Smoking in a household

All data is analysed with IBM SPSS Statistics version 24 (IBM Software, NY, USA, 2016).

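### The immune outcomes are framed as possible IVIg effects but modelled in cohort 2 alone and without older siblings, so any comparison that answers that aim is open to birth-order confounding

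*Combined protocol and SAP*

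**What the plan says.** Section 3.2 places allergies, eczema, asthma and infections under potential long-term side effects of IVIg. Section 9.1.2 gives the purpose of measuring them as the long-term effect of maternal IVIg on the child's immune system.

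Section 11 then locates the analysis: "In second cohort; the FNAIT survivors with IVIg treatment atopic constitution and the course of infections will be assessed in a secondary analysis". It names no comparator.

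- Infections: "In the assessment of course of infections the following confounders will be used in the analysis". The list is day-care, household smoking and time of year.
- Allergies and asthma: "Presence of a first degree family member with asthma eczema or allergy", plus household smoking.

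Section 3.3 is consistent with this. It says "For evaluation of the infections it is important to assess smoking at home and day-care visit as possible confounding factors", and for allergies it names family history. Older siblings, parity and birth order are in neither model, nor among the potential confounders in Table 1 or section 9.1.3. Table 1 does list "Gravidity/Parity", but only as a pregnancy characteristic.

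**The concern.** The way the cohorts are formed probably ties birth order to IVIg exposure. The Summary describes cohort 1 as unanticipated index cases, and the treated group thus: "Second, children with anticipated disease; their mothers were treated with IVIg during pregnancy". Screening is not in place; section 2 says "For 3 decades a nationwide screening on FNAIT to detect pregnancies with alloantibodies in time and start treatment to prevent bleedings is being discussed". Without screening, a pregnancy would normally be recognised as at risk because an earlier one was affected. Cohort 2 should therefore be mostly later-born, while cohort 1 and the general population would include more first-borns.

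The plan already accepts contact with other young children as relevant to infections, because it adjusts for day-care. An older sibling is a similar contact at home. The allergy model has a related weakness: an older sibling is a first-degree relative, so a later-born child has more relatives who can make the family-history covariate positive.

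At stake is a safety statement about IVIg. Depending on the direction of any sibling effect, an unadjusted comparison could suggest harm or give reassurance that birth order explains.

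**Working it through.** **1. The plan's own figure.** The only computed figure is 39 children per cohort, for IQ (section 5.4). A one-sample t-test with SD 15, difference or margin 7 and power 0.8 gives n = 39 at two-sided 0.05 (power 0.811), and n = 39 at one-sided 0.025 with a true difference of zero (power 0.811). It reproduces, and this point does not affect it. It is used below only as a planning size. The plan gives no sample size or precision for the immune outcomes.

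**2. Inputs that the documents do not give.** These are the later-born share in each cohort, the effect of an older sibling on the outcomes, and the comparator. The following are assumptions:

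- later-born share in cohort 2, s2 = 0.95;
- later-born share in the comparator, sc = 0.45 to 0.55;
- risk ratio (RR) for having an older sibling: 1.3, 1.5 or 2.0 for infections, 0.7 for allergy.

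**3. Spurious prevalence ratio when IVIg has no effect.**

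PR = (1 + s2 × (RR − 1)) / (1 + sc × (RR − 1))

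| RR | sc = 0.45 | sc = 0.55 |
|---|---|---|
| 1.3 | 1.285/1.135 = 1.13 | 1.285/1.165 = 1.10 |
| 1.5 | 1.475/1.225 = 1.20 | 1.475/1.275 = 1.16 |
| 2.0 | 1.950/1.450 = 1.34 | 1.950/1.550 = 1.26 |
| 0.7 | 0.715/0.865 = 0.83 | 0.715/0.835 = 0.86 |

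The largest value is 1.345 to three decimals. With s2 from 0.90 to 1.00 and sc from 0.3 to 0.6, the ratio runs from 1.05 to 1.54 for RR 1.2 to 2.0, and from 0.77 to 0.93 for RR 0.7 to 0.8.

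**4. Against sampling error.** Take an illustrative prevalence of 20% and n = 39. The 95% half-width is 1.96 × √(0.2 × 0.8/39) = 12.6 percentage points for one cohort. For a difference between two cohorts of 39 it is 1.96 × √(2 × 0.2 × 0.8/39) = 17.8 points. A ratio of 1.18 (RR 1.5, sc = 0.5) moves 20% to 23.6%, or 3.6 points; a ratio of 1.345 moves it to 26.9%, or 6.9 points. Both lie within these half-widths.

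**5. Would a parity term in the cohort 2 model help?** At s2 = 0.95 the expected number of first-borns is 39 × 0.05 = 1.95, about two children. The standard error of the parity coefficient would be √(0.25/(0.95 × 0.05)) = 2.29 times that of an even split. The model also has no IVIg term to correct, because all its children are exposed.

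**6. Cost of the covariate in a two-cohort model.** Take equal cohorts, s2 = 0.95 and sc = 0.50. The squared correlation of cohort with older sibling is (0.25 × 0.45)² / (0.25 × 0.725 × 0.275) = 0.254. The standard error of the cohort coefficient in a linear model rises by a factor of about √(1/(1 − 0.254)) = 1.16 if the covariate explains no outcome variance.

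**The case against.** The strongest objection is that section 11 contains no comparison to confound. It analyses the second cohort, section 3.2 speaks of determining prevalence, and a model in which every child is exposed estimates no IVIg effect. This stands. A reader might infer that the planned models will return a biased IVIg estimate, but the documents do not support that: the missing comparator is the more basic gap. The concern survives because the stated aim is an effect of IVIg, section 11 calls its covariates confounders, and section 9.3 does not limit the questionnaires to cohort 2.

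Further points against also stand:

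- No section gives the birth order of either cohort. Section 3.1 defines cohort 1 broadly, as all survivors without antenatal treatment, so its first-born share is unknown.
- Nothing in the documents gives the size or direction of a sibling effect. The infection outcome is an indication for immunological work-up, for which no such effect is documented.
- Parity is only a proxy for an older sibling at home, because an earlier affected child may have died. Table 1 does not say whether parity is counted before or after the index birth.
- The assumed shifts are small beside the sampling error at 39 children. That limits their practical weight, but a systematic bias would not shrink with more children.

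**Conclusion.** The point holds in a conditional form. The immune outcomes are meant to inform on IVIg, and a contrast that could do so is open to confounding by birth order, which the plan does not address. On the assumed shares, the spurious ratio is 1.10 to 1.35 for a sibling RR of 1.3 to 2.0, and 0.83 to 0.86 for an RR of 0.7. These figures are illustrations and may lie within sampling error at n = 39.

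Three stronger readings are tempting and are not supported:

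- That cohort 2 is known to be nearly all later-born. This is an inference from anticipated disease without screening, and the sponsor can check it.
- That birth order is tied to IVIg more strongly than day-care or smoking is. The documents give no distribution for any of the three.
- That adding parity to the existing cohort 2 models would solve the problem. It would not, because parity would hardly vary there and no IVIg effect is estimated.

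**What to change.** In section 11:

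1. State cohort 2 versus cohort 1 as the contrast for infections, allergies, asthma and eczema.
2. Include older sibling (yes/no) as a covariate in that two-cohort model, beside the covariates already listed. Derive it from parity before the index birth, or from siblings in the household where known.
3. Add a sensitivity analysis restricted to later-born children in both cohorts.
4. Tabulate parity by cohort, so that the expected imbalance is verified.

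If no contrast is intended, say instead that the cohort 2 prevalences are descriptive and not attributable to IVIg.

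The change takes a few sentences and one covariate from an item already in Table 1, with its timing defined. The cost is precision: a standard error about 16% larger for the contrast on the assumptions in step 6 of the working. In the restricted analysis cohort 1 falls to between 39 × 0.45 = 17.6 and 39 × 0.55 = 21.5 children, about 18 to 21, if it has the assumed comparator share. Some misclassification remains where parity stands in for a sibling at home.

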Outcome	Neurodevelopmental scores	Cognitive test score Motor test score Cerebral palsy Neurodevelopmental impairment Impaired cognitive or motor development Impaired functioning in communication Bilateral blindness Bilateral deafness Quality of life Health related quality of life score Behavior Behavioural test score Academic performance Arithmetic test score at primary school Spelling test score at primary school Reading comprehension test score at primary school Immunology Prevalence of allergies Patient reported anaphylaxis Poor control of allergic rhinitis Poor control of asthma Patient reported eczema Course and incidence of infections
Potential confounders	Demographic characteristics	Age and gender of the child Family history (first degree) of allergy, astma or eczema Highest level of education of the parents Smoking at home Day-care visit Ethnic origin of the parents

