Intracerebral bleeding	Any bleeding in the cerebral cavity.	
Organ bleeding	Bleeding in any organ located in the thorax or abdomen.	
Postpone bleeding	Postpone bleeding that was noted as sign of bleeding by the caretaker.	
Skin manifestations	Petechiae, purpura or hematoma diagnosed by the caretaker at neonatal period (gynecologist, pediatrician or midwife).	
Neonatal IVIG treatment	Any administration of IVIG after birth.	
Platelet transfusion	Any platelet transfusion.	
Neurodevelopmental impairment		
Cerebral Palsy	Spastic bilateral, spastic unilateral or mixed Classification by European CP Network [19].	
Impaired cognitive or motor development	Score < 70 (2 SD below the mean) as assessed by Bayley Scales of Infant and Toddler Development version 3 (BSID III) [16]	
Bilateral blindness	Blind or partially sighted.	
Bilateral deafness	Needing hearing aids.	

Definitions of outcome		(3/3)
Outcome parameter	Definition	
Secondary outcomes		
Abnormal course or incidence of infections	Need to refer to an immunologist or the need to perform diagnostics based on history taking according to the Dutch guidelines. [23]	
Prevalence of allergies	Parent reported allergy.	
Patient reported anaphylaxis	Serious allergic reaction, requiring urgent medical treatment with epinephrine.	
Poor control of allergic rhinitis	CARAT score of upper airways < 8.[22, 33]	
Poor control of asthma	CARAT score of lower airways < 16.[22, 33]	
Prevalence of eczema	Parent reported eczema.	
Demographic characteristics		
Ethnic origin of the parents	Ethnic origin of mother and father.	
Educational level of the parents	Highest level of graduation of the parents.	
Smoking	Any person living in the household of the child smoking one or more cigarettes a day.	
Day-care visit	When child is in day care at least one day a week.	
Family history (first degree) of allergy, asthma or eczema	Positive when 1 st degree of family members receive daily treatment for asthma or eczema. Or when a family member wears an epinephrine pencil because of a severe allergy.	

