12.2 Recruitment and consent

The investigator will identify potential subjects according to the aforementioned criteria.

Eligible patients are informed about the study and are asked for their participation.

Enrolment will take place in two ways;

- First directly via the LUMC, the LUMC is national referral center for intrauterine therapy. Parents of children that survived FNAIT will be invited to participate by sending a patient information letter and information leaflet for children. In this way, the parents will be informed that they will be contacted by phone approximately two weeks after sending the information letter.
- Secondly patients will be asked via Stichting Sanquin Bloedvoorziening, Sanquin is the national reference laboratory to diagnose FNAIT. Retrospectively all FNAIT cases are collected in the Laboratory of platelet and leukocyte serology of Sanquin. Referring specialists (mostly pediatricians) will be asked to obtain permission from the parents to inform them about our study by letter enclosed by the patient information leaflet. If parents do not object to be informed they will be contacted by our research team approximately two weeks after sending this letter.

When parents wish not to be approached by our research team they can indicate this by responding by e-mail, phone or reply letter. Informed consent is obtained from all patients who are willing to participate. In case of minors both parents or their guardian will be asked for participation and informed consent. The patient information letter and informed consent form will be attached as a separate document. If informed consent is given, assessment will be planned. At most, 3 attempts will be made to contact parents by phone. It is expected that enrollment for this study will cover a period of one year.

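### Age is in neither immune-outcome model and season is missing from the allergy/asthma model, so cohort 2's immune estimates partly depend on age mix and its CARATkids results on season mix

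*Combined protocol and SAP*

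**What the plan says.** Section 11 places the immune outcomes in one cohort: "In second cohort; the FNAIT survivors with IVIg treatment atopic constitution and the course of infections will be assessed in a secondary analysis". It names no comparator for them. Two covariate lists follow.

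- Infections: "In the assessment of course of infections the following confounders will be used in the analysis by using a linear regression model". The list is day-care, household smoking and "Time of the year that the questionnaire was filled in".
- Allergies and asthma: "In the analysis of allergies and asthma the following confounders will be used in the analysis by using a linear regression model". The list is "Presence of a first degree family member with asthma eczema or allergy" and household smoking.

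Table 1 (Section 3.3) puts "Age and gender of the child" under potential confounders, beside family history, smoking and day-care. Section 5.2 admits children aged 2 to 16. On timing, Section 12.2 says "It is expected that enrollment for this study will cover a period of one year".

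Section 9.1.2 describes CARATkids in the same bullet as the prevalence of allergies, asthma and eczema. Table 2 uses it for the severity of asthma and hay fever from age 6. Table 3 turns the upper- and lower-airway scores into poor-control outcomes, with cut-offs of below 8 and below 16.

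**The concern.** The plan accepts, for infections, that the time of year at which a parent fills in a form can affect the answer. It does not carry this over to a control score for hay fever, for which the same reasoning is at least as strong. It also lists age as a potential confounder and then uses it in neither immune model, over an age span of fourteen years.

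Section 3.2 gives the purpose of these outcomes as potential long-term side effects of IVIg. An estimate that moves with the ages of the children who attended, or with the months in which they attended, serves that purpose less well. A reader could not tell how much of a high or low figure belongs to the mix of children and visits.

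**Working it through.** The documents give no rates for these outcomes, so there is no planned figure to reproduce. The check sets the covariate lists against the other sections, then uses assumed rates to show what order of effect is possible.

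**Covariates, side by side**

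- Season: in the infection list; not in the allergy/asthma list.
- Age at assessment: in neither list.
- Household smoking: in both.
- Day-care: infections only. Family history: allergies and asthma only.

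**Is season or age handled elsewhere?** No section provides stratification, age-specific reference values or a fixed season for the immune questionnaires.

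**Where do the CARATkids scores belong?** Section 11 does not name them. Section 9.1.2 and Table 2 put them with allergy and asthma, and no other model is given. Their place in the allergy/asthma model is therefore an inference.

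**Why age matters more here than for IQ.** The Summary says cognition is measured with standardized tests appropriate for age. Allergy and eczema are parent reports, and the infection outcome is a yes/no indication for evaluation by an immunologist (Tables 2 and 3). Nothing in the protocol scales these to age.

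**Illustration for season (rates and shares are assumptions).** Let f be the share of children whose questionnaire falls in season. The crude rate of poor rhinitis control is

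p = p_off + f × (p_on − p_off)

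- Rates 10% off and 20% in season: f = 0.10 gives 11%; f = 0.75 gives 17.5%. Range 6.5 points.
- Rates 10% and 30%: 0.10 + 0.10 × 0.20 = 12%; 0.10 + 0.75 × 0.20 = 25%. Range 13 points.
- Rates 20% and 50%: 0.20 + 0.10 × 0.30 = 23%; 0.20 + 0.75 × 0.30 = 42.5%. Range 19.5 points.

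**Sampling error for comparison.** With the 39 children planned for cohort 2 (Section 5.4), the 95% half-width is 1.96 × √(p(1 − p)/39): 9.4 points at p = 10%, 12.6 at 20% and 14.4 at 30%. CARATkids starts at age 6, so its number would be smaller and its intervals wider. Under uneven timing the shift could be as large as the sampling error.

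**Even timing.** If visits are spread evenly and a third of the year counts as in season, f has a standard deviation of √(1/3 × 2/3 / 39) = 0.075. With a 20-point seasonal difference that moves the rate by about 0.075 × 20 = 1.5 points. Even timing therefore makes the season effect small.

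The same formula holds for age, with f as the share of younger children. Even timing does nothing to reduce that effect.

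**The case against.** Several parts of the opposing case stand.

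- **No contrast is specified.** Section 11 analyses these outcomes in cohort 2 alone. A reader might infer that the estimated effect of IVIg is already confounded by age and season. That needs a comparison with cohort 1 or a reference, and Section 11 names neither. What can be said now is that the estimate depends on case mix.
- **Season reaches less than it seems.** A reader might infer that all the immune results reflect when a child was seen. The infection model already has time of year, and Table 3 gives parent-reported allergy and eczema no time window. The season point is mainly about CARATkids, from age 6.
- **Age was not clearly promised for these models.** The text of Section 3.3 links age and sex to neurodevelopmental outcome and names other confounders for allergies and infections. Table 1 alone does not make the omission a broken commitment. Even so, listing age as a confounder and then using it in neither immune model leaves a gap.
- **The infection outcome is guideline-based.** Whether the cited criteria already allow for age cannot be judged from the documents.
- **Cohort 2 need not be younger.** One might argue that anticipated pregnancies follow an earlier affected child, so cohort 2 is younger at assessment. The documents give no age distribution, and both cohorts share the 2002 to 2017 birth window.
- **Day-care is at most a partial proxy for age.** Its definition, "When child is in day care at least one day a week", is in the present tense and so plausibly tracks age. Nothing shows that its coefficient largely stands in for age.

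Extra terms also cost precision in a cohort of about 39. That bears on the form of the remedy and does not remove the inconsistency.

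**Conclusion.** The point holds for secondary outcomes. Followed as written, Section 11 leaves the allergy, asthma, eczema and infection outcomes unadjusted for age across ages 2 to 16, and the CARATkids control scores unadjusted for season. The cohort 2 estimates will partly depend on the age mix, and the CARATkids results on the season mix, of the children seen.

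The size is unknown. The assumed rates above give shifts from 6.5 to 19.5 points for extreme differences in the in-season share, and about 1.5 points under even enrolment with a 20-point seasonal difference. The season part rests on the inference that the allergy/asthma model covers CARATkids. The primary IQ analysis is not affected.

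**What to change.** In Section 11:

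- Add age at assessment to both the infection and the allergy/asthma models.
- Add time of year of questionnaire completion to the CARATkids analyses, and state which model those scores belong to.
- If numbers are too small for the extra terms, report these outcomes by age band and season instead.
- Reconcile Table 1 with the covariate lists.

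No new data are needed. Age is already collected (Section 3.3). The infection model already requires the questionnaire date, and under Section 9.3 the allergy and infection questionnaires are sent home to be brought to the same visit. The cost is one or two more model terms in a small cohort.

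Covariates alone will not make a one-group prevalence interpretable as an effect of IVIg. If a comparison is intended, the plan should name it, and any external reference should match on age and, for CARATkids, on season.
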